## Section F. Participants

### 1. Description of research participants

56 healthy volunteers aged 18-45

### 2. Inclusion Criteria

- Participant is willing and able to give informed consent for participation in the research
- Not currently taking any medications which may interfere with pitolisant, including psychoactive medications
- Not currently using antihistaminergic medication
- Aged 18-45 years
- Male or female
- Sufficiently fluent English to understand and complete cognitive tasks and questionnaires
- Body Mass Index above or below 18-30
- Right handed

### 3. Exclusion criteria

The participant may not enter the study if ANY of the following apply:

- Current pregnancy (as determined by urine pregnancy test taken during screening visit), planning to become pregnant or breast feeding
- Any past or current history of severe and/or serious psychiatric disorder, including but not limited to schizophrenia, psychosis, bipolar affective disorder, major depressive disorder, obsessive compulsive disorder

- Clinically significant abnormal values for urine drug screen, blood pressure measurement ( in accordance with AP20 ‘non-invasive blood pressure’) and ECG. A participant with a clinical abnormality or parameters outside the reference range for the population being studied may be included only if the Investigator considers that the finding is unlikely to introduce additional risk factors and will not interfere with the study procedures
- History of, or current medical conditions which, in the opinion of the investigator, may interfere with the safety of the participant or the scientific integrity of the study, including epilepsy/seizures, brain injury, hepatic or renal disease, acid-related gastro-intestinal problems, Central Nervous System (CNS) tumours, neurological conditions
- Current or past history of drug or alcohol dependency
- Severe lactose intolerance
- Use of recreational drugs (e.g. cannabis, cocaine, amphetamines) within past 3 months
- Participation in a study which uses the same computer tasks as those in the present study (determined by asking participants about previous studies participated in during screening) within past 3 months
- Participation in a study that involves the use of a medication within the last three months
- Smoking > 5 cigarettes per day
- Consumption of a high amount of caffeine per day (> 400ml caffeine) (e.g., 5 or more cups of coffee)
- Participant is unlikely to comply with the clinical study protocol or is unsuitable for any other reason, in the opinion of the Investigator
- Any contraindication to MRI scanning (e.g. metal objects in your body, pacemakers, significant claustrophobia)
- Not right handed

#### 4. Recruitment

Participants will be recruited from the general population by using posters (with rip-off tabs) and advertisements in the local press and on the internet (see APPENDIX A - STUDY ADVERT; APPENDIX N - STUDY ADVERT TOKENS (TO TAKE FROM POSTER)). Adverts will be sent to Junior Common Rooms and Middle Common Rooms, displayed in colleges and university departments and local community buildings. Adverts may also be placed on local information websites (e.g. Daily Info, Oxford University Gazette), newspapers, local magazines, on the radio and on the lab webpage, and online advertisements via Call for Participants (<https://www.callforparticipants.com/>) and Meta adverting (Facebook and Instagram) – with text and imagery adapted from only the information provided in ‘APPENDIX A - STUDY ADVERT’. The adverts will contain brief information about the inclusion criteria for the study, as well as contact details for the named researchers.

After a potential volunteer has contacted the research team to indicate potential interest, they will be sent the Participant Information Sheet via email. The participant will be given as much time as they need to decide within reasonable limits whether they would like to take part, and will be invited to ask any questions that they have about the study. If the participant decides that they do not want to take part in the study, they will be thanked for their interest and there will be no further contact from the research team. If the participant decides they would like to take part, they will be invited for a screening visit at the Department of Psychiatry, Warneford Hospital. At the beginning of this visit, one of the named researchers will explain the study to the participant and answer any questions that he/she has. The researcher will then take written consent from the participant. All of the named researchers have been trained in taking informed consent.

#### 5. Eligibility assessment

Screening eligibility for study participation occurs at two time-points:

**Online screening:**

Consent to participate in the online screening will be sought initially, where participants will be provided with a copy of the Participant Information Sheet (see APPENDIX F: PARTICIPANT INFORMATION SHEET)

and required to give informed consent in accordance with the statements on Informed Consent Form (APPENDIX G: INFORMED CONSENT FORM). Consent will be collected on the Qualtrics system via digital signature entry. Participants will be informed that further written consent will need to be obtained at a later date at the first in person visit (screening visit). After consent is obtained, an automated online screening (via Qualtrics) will occur which will ask participants to provide the following details;

- History of medical and psychiatric difficulties (incl. family history where appropriate).
- Age
- Current and past medication use (incl. use of recreational drugs).
- Handedness
- Basic MRI screening form for contraindications check (e.g. surgically implanted metal objects or pacemakers)
- Prior participation in research studies in the Department of Psychiatry and/or Department of Experimental Psychiatry

In instances where a participant selects an option that could suggest ineligibility on the Qualtrics questionnaire, Qualtrics would then route them to a free-text box to provide further information. Qualtrics reports will be parsed and then checked if participants are eligible to proceed to the next screening visit. Please find the Qualtrics questionnaire details in 'APPENDIX B - ONLINE CONSENT FORM (QUALTRICS PRINT)' and 'APPENDIX D - ONLINE SCREENING FORM (QUALTRICS PRINT)'.

#### **Screening visit:**

Participants who met the eligibility criteria during the online screening then would be invited to book themselves into an in-person screening visit occurring at the Neurosciences Building, Warneford Hospital Site. The visit will take approximately 60-90 minutes to complete. A physical copy of informed consent will be taken at the start of visit as the consent obtained during the online screening would have been done remotely. The screening visit involves the following procedures (APPENDIX J - SECONDARY SCREENING FORM):

- Personal contact details collection (paper)
- MRI Screening Form (APPENDIX H - 3T VOLUNTEER SCREENING FORM)
- Further demographic data including gender and years in education
- Weight, height measurement
- Vital signs assessment (blood pressure and ECG to check for heart electrical abnormalities)
- 12 lead ECG
- Urine drug screening
- Urine pregnancy test
- Working memory task (to assess baseline cognitive ability for randomisation procedure)
- SCID-V Interview (Structured clinical Interview for DSM-V, a set of standard clinical questions asking about current and past psychiatric illness)

All physical health assessments will be overseen by the study medical officer ([name]) or other delegated medical professional. For the ECG assessment, a chaperone will be offered to participants according to the risk assessment. All clinical procedures in this study will be carried out following a study-specific and WIN-specific risk assessments, particularly pertaining to COVID-19 risk (APPENDIX C - NEUROSCIENCES BLDG RISK ASSESSMENT; APPENDIX L – WIN RISK ASSESSMENT FOR RTOSW) If participants fit the study criteria they will then be invited for the second visit: 'Study visit'. A maximum of six weeks is allowed between the Screening Visit and the Study Visit. If this duration is exceeded, another screening will be performed to ensure eligibility.

## **6. Information Provided to Participants and Informed Consent**

The Participant Information Sheet (see APPENDIX F: PARTICIPANT INFORMATION SHEET) will be presented to the participants, and verbally communicated to participants (in-person screening). Both will detail the exact practical demands of the study, written from the participant's perspective, in lay language (the nature of the study, what it will involve for the participants, the implications and constraints of the protocol, the known side effects and any risks involved in taking part, what will happen to the data collected). It will be clearly stated that the participant is free to withdraw from the study at any time for any reason and with no obligation to give the reason for withdrawal.

The participant will be allowed as much time as they wish to consider the information, and the opportunity to ask question the Investigator, their General Practitioner (GP) or other independent parties to decide whether they will participate in the study.

A physical copy of the latest approved version of the Informed Consent Form (ICF; see APPENDIX G: INFORMED CONSENT FORM) that participants consented to at the online screening (via digital signature on Qualtrics) must be signed by participants during the screening visit. This will be done before any study-specific procedures are performed.

Written Informed Consent will then be obtained by means of participant dated signature and dated signature of the person who presented and obtained the Informed Consent. The person who obtained the consent will be suitably qualified and experienced, and have been authorised to do so by the Principal Investigator (PI). A copy of the signed ICF will be given to the participant. The original signed form will be retained at the study site. During the online Screening Visit, an electronic version of the ICF will be completed and then a paper version will be completed at the start of the in-person screening Visit (see Section F5).

Due to the ongoing COVID-19 pandemic, study participants will be provided with guidelines for how to adhere to the latest social guidance policy (see APPENDIX K: COVID-19 GUIDELINES FOR RESEARCH PARTICIPANTS). As the situation is ongoing, participants will be updated by the researchers if the guidelines change and provided an updated guidelines document.

## Section G. Research Procedures

### 1. Baseline Assessments and Procedures

Baseline assessments and procedures will take place at the online screening and screening visit. They will consist of the following:

#### **Online screening:**

Consent to participate in the online screening will be sought initially, where participants will be provided with a copy of the Participant Information Sheet (see APPENDIX F: PARTICIPANT INFORMATION SHEET) and required to give informed consent in accordance with the statements on Informed Consent Form (APPENDIX G: INFORMED CONSENT FORM). Consent will be collected on the Qualtrics system via digital signature entry (APPENDIX B - ONLINE CONSENT FORM (QUALTRICS PRINT)). Participants will be informed that further written consent will need to be obtained at a later date at the first in person visit (screening visit). After consent is obtained, an automated online screening (via Qualtrics) will occur which will ask participants to provide the following details;

- History of medical and psychiatric difficulties (incl. family history where appropriate).
- Age and other demographic information including gender
- Estimation of weight and height
- Current and past medication use (incl. use of recreational drugs).
- Handedness
- Basic MRI screening form for contraindications check (*e.g.* surgically implanted metal objects or pacemakers)
- Prior participation in research studies in the Department of Psychiatry and/or Department of Experimental Psychiatry

In instances where a participant selects an option that could suggest ineligibility on the Qualtrics questionnaire, Qualtrics would then route them to a free-text box to provide further information. Qualtrics reports will parsed

and then checked if participants are eligible to proceed to the next screening visit. Please find the Qualtrics questionnaire details in 'APPENDIX D - ONLINE SCREENING FORM (QUALTRICS PRINT)'.

### **Screening visit:**

Participants who met the eligibility criteria during the online screening then would be invited to book themselves into a screening visit occurring at the Neurosciences Building, Warneford Hospital Site. The visit will take approximately 60-90 minutes to complete. A physical copy of informed consent will be taken at the start of visit as the consent obtained during the online screening would have been done remotely. The screening visit involves the following procedures:

- Personal contact details collection (paper)
- Weight, height measurement
- Vital signs assessment (blood pressure and ECG to check for heart electrical abnormalities)
- 12 lead ECG
- Urine drug screening
- Urine pregnancy test
- Digital Span Task – Forward/Backwards (to assess baseline cognitive ability for randomisation procedure); this task will require participants to repeat a sequence of numbers in a particular order (forwards or backwards) orally to the researcher.
- SCID-V Interview (Structured clinical Interview for DSM-V, a set of standard clinical questions asking about current and past psychiatric illness)
- MRI screening form

All physical health assessments will be overseen by the medical officer attached to this study ([name]) or other delegated medical professional. For the ECG assessment, a chaperone will be offered to participants according to the risk assessment. All clinical procedures in this study (including COVID-related restrictions) will be carried out following a study-specific risk assessment and in adherence to the standard operating procedure of Neurosciences Building risk assessment (see APPENDIX C - NEUROSCIENCES BLDG RISK ASSESSMENT). If participants fit the study criteria they will then be invited for the second visit: 'Study visit'. A maximum of four weeks is allowed between the Screening Visit and the Study Visit. If this duration is exceeded, another screening will be performed to ensure eligibility.

## **2. Subsequent Visits**

### Study Visit

Participants who are medically approved to take part in the study after the screening visit are invited to take part in the study visit. Prior to the study visit, and after the screening visit, participants will be randomised using the variance minimisation algorithm described above to ensure a balance of covariates of interest across treatment and placebo groups. The randomisation code will be drawn up by a researcher not involved in the study using an randomisation procedure known as variance minimisation, following a procedure outlined by Sella, Raz & Cohen Kadosh (2021). Participants will be allocated to placebo or treatment groups based on gender, level of education, and their digit span score (as an index of general intelligence). Allocation of treatments will be recorded on a Randomisation List which will be updated when each new participant enters the randomised phase. The Randomisation List will be held securely within the Neurosciences Building by the study medic ([name]). Pitolisant and placebo agents will be kept securely within a locked medicines cabinet also within the Neurosciences building.

During the visit, participants will receive either a single dose of pitolisant (36mg single dose) or placebo. They will receive the dose at the Neurosciences Building, Warneford Hospital site. The study has a double-blind design thus neither the researchers nor the participant will know whether pitolisant or placebo is given. On arrival, participants will briefly be reviewed to ensure the inclusion criteria are still satisfied. Prior to drug or placebo administration, the following procedures will be undertaken:

- Inclusion/exclusion criteria review

- Completion of the MRI screening form (APPENDIX H - 3T VOLUNTEER SCREENING FORM) once more to ensure it is still safe for them to undergo fMRI scanning.
- Clinical screening, mood and side effects questionnaires (to establish baseline) on qualtrics – PHQ-9, GAD-7, PANAS, PDQ and Need for Cognition Scale

Providing eligibility still holds following review, participants will then take the single dose of pitolisant or placebo. There will then be a two-hour monitoring period to allow for the drug (where appropriate) to metabolise and activate within the system. Participants will then be escorted to OHBA where they will undertake an MRI scan (or, fMRIB if nil capacity at OHBA). First participants will be asked to change into MRI safe scrubs and screened for MRI safety by the scan operator / radiographer. MRI scans will be undertaken in accordance to the CUREC approved MRI scanning procedure (APPENDIX M - CUREC APPROVED MRI INVESTIGATIONS PROCEDURE). The scan itself will include:

- Structural scan (T1 and T2-weighted imaging)
- Probabilistic Learning Task (fMRI) – this task requires participants to choose one of two pairs of symbol every trial. One of these pairs will be associated with a win probability and the other not, with each pair corresponding to reciprocal probabilities. Participants are asked to make choices based on what symbol will maximise their win-loss ratio and increase monetary outcome. Participants will be instructed that they will be reimbursed at the end of the study based on their performance during this task (participants can win up to £20 total depending on performance).
- Memory task (fMRI) – This task requires participants to learn presented emotionally neutral stimuli (images) prior to the scan, then during the scan they will be asked to recall if the stimuli presented during the scan were previously seen using a two-button press.
- Verbal *n*-back task (fMRI) – it will require participants to concentrate on a series of letters (upper case and lower case) stimuli displayed centre-screen and pressing a button according to a rule provided before each block (e.g. press spacebar if you see an image you previously saw three images ago).
- Resting State fMRI – this will not require participants to perform any tasks and will take approximately 7 minutes to complete
- Arterial spin labelling
- Physiological recordings including pulse, respiration, and skin conductance – recorded using a pulse meter, respiration bellows and electrodes strapped by Velcro to fingertips.
- Eye tracking

Once the scanning has completed (approximately 1.5 hours), participants will be escorted back to the Neurosciences Building, Warneford Hospital site. Here, participants will complete the remaining:

- Affect, Mood, Subjective Cognition and Side Effects questionnaires (for end-point):
  - PHQ-9
  - GAD-7
  - Visual Analogue Scale
  - Perceived Deficits Questionnaire
  - Side Effects Questionnaire
  - PANAS
  - Need for Cognition Scale
- Instrumental *n*-back task – this widely used task will be done after scanning is complete; it will require participants to complete a version of the *n*-back task in the scanner, but this time participants are rewarded or punished for performance. Participants will start with £1.00 and can earn up to £10 based on performance (similar to the PILT), but cannot lose less than £0.00. This task will involve more complex levels of working memory processing (including 4-back, 5-back).
- A change detection task – a short task of visual working memory which requires participants to view an array of ‘items’ (e.g. coloured blocks) for a short period of time, and after a short period they are shown the same array once again with one subtle change (e.g., one colour has been changed). Participants must identify the change.

- Emotional Go/No-Go task (EGNG) -- this task follows a 'go/no-go' format where participants will be presented stimuli on-screen which they are instructed to either press a button for 'go' trials or inhibit their response. Emotional and non-emotional distractors will be used to check the effect of emotional distraction on response inhibition.
- Facial Emotional Recognition Task (FERT) – the widely-used task will ask participants to recognise the emotion of faces displayed on the screen in sequence; emotions include: sad, surprised, angry, disgusted, happy, neutral).

Once participants had completed these procedures then the study visit will end. Before leaving, participants will be given a wallet-sized card with key details about the study and contact information of a member of the study team to contact if they have any questions. The card will also include the phone number of the out-of-hours BRC on-call medic service in case they need medical advice related to the study out of standard office hours. At the end of this visit, participants will be advised not to drive, cycle or operate machinery, in case they experience any side effects from the drug. To ensure participants get home safely after the visit, the researcher will either arrange a taxi or travel expenses (e.g. bus tickets) for the journey will be reimbursed.

Participants will be followed-up the day following the study visit with a mood/side effects questionnaire in addition to debriefing and reimbursement details processing. This follow-up should between 30-45 minutes to complete.

The cognitive tasks include measures of executive functioning, decision making and memory. Memory ability is measured through the fMRI memory and instrumental n-back tasks, both of which require participants to recall presented stimuli at a later date. The EGNG will measure response inhibition (executive functioning), requiring participants to continuously press a keyboard input while occasionally being prompted to inhibit their response; this task will rely on affective prompts (e.g. a face with a particular emotional expression) or non-affective prompts (e.g. a phrase such as "do not press spacebar"). The FERT measures emotional processing, and involves the presentation of faces displaying different emotions. In another task of instrumental learning (PILT), participants will be asked to choose between shapes, some of which lead to winning money and some of which lead to losing money – participants will be able to win up to £10 which will be added to the reimbursement they receive at the end of the study. All stimuli will be presented on a computer screen and participants will be required to respond via button presses on a keyboard.

Mood questionnaires are short self-report inventories, including PHQ-9, GAD-7, Need for Cognition Scale, and Positive and Negative Affect Scale.

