### 5. Discontinuation/Withdrawal of Participants

Each participant has the right to withdraw from the research at any time. In addition, the Investigator may discontinue a participant from the research at any time if the Investigator considers it necessary for any reason including:

- Pregnancy
- Ineligibility (either arising during the research or retrospectively having been overlooked at screening)

- Significant protocol deviation
- Significant non-compliance with treatment regimen or research requirements
- Withdrawal of consent
- Loss to follow up

If a participant is withdrawn, no further procedures or observations will continue to be required. Withdrawal from the study will result in exclusion of the data for that participant from analysis. Withdrawn participants will be replaced. The reason for withdrawal if given will be recorded in the Participant Log of the Research Master File.

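### Participants are allocated, and the arm recorded on a list held by the study medic, before the arrival review that decides dosing; this is an avoidable weakness in concealment, cheaply removed

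*Protocol*

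**What the plan says.** Section G.2 (Study Visit) has a researcher outside the study draw up the randomisation code. On timing it says: "Prior to the study visit, and after the screening visit, participants will be randomised using the variance minimisation algorithm". On the record of allocations: "Allocation of treatments will be recorded on a Randomisation List which will be updated when each new participant enters the randomised phase". On custody: "The Randomisation List will be held securely within the Neurosciences Building by the study medic".

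The same section describes a later eligibility check: "On arrival, participants will briefly be reviewed to ensure the inclusion criteria are still satisfied". Dosing depends on it: "Providing eligibility still holds following review, participants will then take the single dose of pitolisant or placebo". No reviewer is named for this check.

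On blinding, the section states: "The study has a double-blind design thus neither the researchers nor the participant will know whether pitolisant or placebo is given".

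Three other places bear on the point:
- Section G.5 lists among the grounds for discontinuation "Ineligibility (either arising during the research or retrospectively having been overlooked at screening". It excludes a withdrawn participant's data from the analysis and replaces the participant.
- Section H has drug and placebo dispensed by either a study medic or a nurse. Both agents are put into opaque capsules by trial support staff under a standard operating procedure.
- Section I.3, item 2 gives the study medic or a delegate access to the code for emergency unblinding, one participant at a time and within 1 hour.

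**The concern.** Concealment should last until the decision to enter a participant can no longer be changed. Here the arm is assigned and written down first, and a check that can still turn the participant away comes second. Someone who had seen the list could, without intending to, let the arm influence a borderline decision at that check. A participant removed in this way drops out of the analysis and is replaced, so the final data set would not show the removal.

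What is at stake is selection after allocation. Rating of outcomes by the medic is not at issue, because the outcomes are computer tasks, imaging and self-report. A lesser matter is the blinding sentence, which names no unblinded role although a study role holds the list.

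**Working it through.** The point is procedural. No figure in the protocol measures it and no bias can be calculated, so the check is to put the stated steps in order.

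| Step | What happens | Where | Who |
|---|---|---|---|
| 1 | Screening assessments; a doctor's final judgement on inclusion | Sections G.1 and I.3 item 3 | Medical officer or delegate; a doctor in the research team |
| 2 | Code drawn up | Section G.2 | Researcher not involved in the study |
| 3 | Participant allocated and allocation recorded | Section G.2 | Person updating the list not stated |
| 4 | List held | Section G.2 | Study medic |
| 5 | Eligibility reviewed on arrival | Section G.2 | Not stated |
| 6 | Dose dispensed if step 5 is passed | Sections G.2 and H | Study medic or nurse |
| 7 | If withdrawn: data excluded, participant replaced | Section G.5 | Not applicable |

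**Order.** Step 3 precedes step 5, and step 6 depends on step 5. The arm therefore exists on paper during a check that can still exclude. This holds for every one of the 56 planned participants (28 per group).

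**Roles.** Step 4 is assigned to the study medic. Step 5 is assigned to nobody, and step 6 may fall to a study medic. No sentence keeps the holder at step 4 away from steps 5 or 6. The outside researcher at step 2 protects the generation of the code. It does not protect what happens once the allocation is on the list.

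**Discretion at step 5.** The arrival visit includes a review of the inclusion and exclusion criteria. One exclusion criterion in Section F.3 is a matter of judgement: "Participant is unlikely to comply with the clinical study protocol or is unsuitable for any other reason, in the opinion of the Investigator". The review is therefore not wholly objective, although how much judgement is used in practice cannot be read from the document.

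**Consequence at step 7.** Ineligibility that arises during the research is a ground for discontinuation. Taking a participant turned away on arrival to fall under that rule, the data are excluded and a replacement enters.

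**Blinding sentence.** Whether it covers the medic depends on who counts as a researcher. Section I.3 item 3 places a doctor within the research team, whereas item 5 mentions the medic covering the visit as an alternative to a member of that team. The protocol does not settle it.

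**The case against.** The strongest reply is that this argues from silence. No sentence makes the list holder the arrival reviewer or the dispenser, and a nurse may dispense. Names are removed from this copy, so it cannot show whether one person fills several roles. Secure custody is neither upkeep of the list nor routine viewing of it. Emergency code access for a medic is ordinary practice, and Section I.3 limits it to the individual concerned. Opaque capsules protect the blind at dosing. Participants are medically approved before they are randomised, and the arrival check is described as brief. All of this stands, and it limits the point to a missing safeguard.

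A reader might infer that the blind is broken, or that the medic selects participants knowing their arm. The documents do not support that, for the reasons just given. They also do not show that packs are uncoded.

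A reader might also count the exclusion criteria that refer to the investigator's opinion, 3 of 14, and treat the share as the size of the problem. It is not. Medical approval has already used up much of that discretion. In the criterion on abnormal values, the investigator's opinion serves to admit a participant, not to refuse one. Nor does the weight of one replaced participant in an arm measure bias, and the protocol gives no expected number of arrival rejections.

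Finally, a reader might call the blinding sentence false. That goes too far, because it is unclear whether its wording includes the medic.

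The reply does not remove the stated sequence. The protocol itself fixes allocation before the review and places the list with a study role, and both can be changed easily.

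**Conclusion.** The protocol fixes a sequence that is weaker than it need be: allocation and recording of the arm, then a review that can still exclude, then exclusion from analysis and replacement of anyone withdrawn. The list is in the custody of a study role that is not separated from the review or from dispensing. This is an avoidable weakness in concealment and not a shown breach.

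Any effect on the results is unquantified and probably small. The conclusion rests on two readings: that the list shows actual arms, since no coding of it is described, and that a participant turned away on arrival is handled as a withdrawal under Section G.5. If the list were coded and the list holder had no part in the review or dispensing, little would remain beyond a clarification of wording. The change is a cheap improvement of optional severity.

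**What to change.** - In Section G.2, assign or release the allocation only after the arrival review is passed. Alternatively, state that the review is done by someone without access to the list.
- Let the uninvolved researcher who draws up the code also hold and update the Randomisation List.
- Give the study medic individual code-breaks in place of the list, reachable within the 1 hour already set in Section I.3.
- In the blinding sentence, state whether the medic is an unblinded role.

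The cost is mostly wording, because the uninvolved researcher is already part of the procedure. The downside is some study-day logistics: the allocation or a prepared pack must be available as soon as the review is passed, and the code-breaks must be to hand. The sample size is unaffected.
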